Appendix C Measurement of Blood Pressure and Pulse Rate

Equipment

1. Blood pressure measurements will be taken by an automated BP monitor or a manual sphygmomanometer. The same equipment should be used throughout the study and should be calibrated as per manufacturer recommendation
2. Bladder Length – Should nearly or completely encircle the patient's arm. For many adults, the standard "adult" size bladder is not long enough and the "large" size bladder is recommended
3. Bladder Width – Should be at least 40% of the bladder length

Patient Factors

Extraneous variables associated with the measurement of BP should be minimized. These include:

1. Food intake, caffeine-containing beverages, cigarette smoking, or strenuous exercise within 2 hours prior to measurement
2. Full urinary bladder
3. The patient should not be allowed to talk while BP is being measured
4. The patient should be placed in the examination room and the cuff should be placed on the patient's nondominant arm. The proper sized cuff should fit snugly with the lower edge 2 to 3 cm above the antecubital fossa
5. The patient should be allowed to sit quietly in a comfortably warm place (temperature around 25°C or 77°F) for 5 minutes with the arm supported at heart level, preferably with the cuff in place and with no restrictive clothing on the arm. The patient should be encouraged not to tense his or her muscles

Nondominant Arm

The patient's nondominant arm should be the arm declared by the patient as being nondominant. The nondominant arm should then be used for all seated BP measurements throughout the study.

Measurement Technique

[figure not shown]
At all other on-site visits, following the 5-minute rest period, 3 separate seated BPs should be measured in the arm selected at Visit 1, with at least 1 minute between BP measurements and with the cuff fully deflated between measurements.

All 3 BPs will be recorded in the patient's electronic case report form (e-CRF). The mean of the 3 seated BPs will constitute the BP value for that visit.

Three seated pulse rate measurements will be obtained. The mean of the 3 seated pulse rate measurements will constitute the pulse rate value for that visit.

Appendix D General guidance for the follow-up of laboratory abnormalities by Sanofi

NEUTROPENIA

[figure not shown]

Note:

- The procedures described in the above flowchart are to be discussed with the patient only in case the event occurs. If applicable (according to local regulations), an additional consent (e.g., for HIV testing) will only be obtained in the case the event actually occurs.
- For individuals of African descent, the relevant value of concern is <1000/mm³

Neutropenia is to be recorded as an AE only if at least 1 of the criteria listed in the general guidelines for reporting adverse events in [Section 10.4.2](#) is met.

[figure not shown]
THROMBOCYTOPENIA

Note:

The procedures above flowchart are to be discussed with the patient only in case described in the the event occurs. If applicable (according to local regulations), an additional consent (e.g., for HIV testing) will only be obtained in the case the event actually occurs.

Thrombocytopenia is to be recorded as an AE only if at least 1 of the criteria listed in the general guidelines for reporting adverse events in [Section 10.4.2](#) is met.

[figure not shown]

- In ANY CASE, FOLLOW** the instructions listed in the box below:
1. **INFORM** the Site Monitor who will forward the information to the Study Manager
 2. **INVESTIGATE** specifically for malaise with or without loss of consciousness, dizziness, and/or hypotension and/or episode of arrhythmia in the previous 72 hours; rule out muscular injury
 3. **PERFORM** the following tests:
 - LFTs: AST, ALT, alkaline phosphatase, total and conjugated bilirubin and prothrombin time / INR
 - CPK, serum creatinine, complete blood count
 - Anti-HAV IgM, anti-HBc IgM (HBV-DNA if clinically indicated), anti-HCV and HCV RNA, anti-CMV IgM and anti-HEV IgM antibodies
 - Depending on the clinical context, check for recent infection with EBV, herpes viruses, and toxoplasma
 - Hepatobiliary ultrasonography (or other imaging investigations if needed)
 4. **CONSIDER** Auto-antibodies: antinuclear, anti-DNA, anti-smooth muscle, anti-LKM
 5. **CONSIDER** consulting with hepatologist
 6. **CONSIDER** patient hospitalisation if INR>2 (or PT<50%) and/or central nervous system disturbances suggesting hepatic encephalopathy
 7. **MONITOR LFTs after discontinuation of IMP:**
 - As closely as possible (or every 48 hours) until stabilization, then every 2 weeks until return to normal/baseline or clinical resolution.
 8. **FREEZE** serum sample (5ml x 2)

**VERSION HISTORY**

Version Status	Version Date
Final 1.0	07 August 2018
Final 2.0	03 June 2019
Final 3.0	19 February 2020

## LIST OF ABBREVIATIONS AND DEFINITION OF TERMS

AEs:	adverse events
AESI:	adverse events of special interest
ALT:	alanine aminotransferase
ANCOVA:	analysis of covariance
AST:	aspartate aminotransferase
BLOQ:	below limit of quantification
ATC:	anatomical therapeutic chemical
BMI:	body mass index
BUN:	blood urea nitrogen
CEC:	clinical endpoint committee
CI:	confidence interval
CMH:	Cochran-Mantel-Haenszel
CV:	cardiovascular, cardiovascular
DBP:	diastolic blood pressure
DCCT:	diabetes control and complications trial
DILI:	drug-induced liver injury
DMC:	Data Monitoring Committee
ECG:	electrocardiogram
e-CRF:	electronic case report form
eGFR:	estimated glomerular filtration rate
EMA/PRAC:	European Medicines Agency/ Pharmacovigilance Risk Assessment Committee
EOSI:	events of special interest
EOT:	end of treatment
FPG:	fasting plasma glucose
Gd:	glibenclamide
GdMR:	glibenclamide MR
Gp:	glipizide
GpXL:	glipizide XL
Gz:	gliclazide
GzMR:	gliclazide MR
HbA1c:	hemoglobin A1c
HLGT:	high level group term
HLT:	high level term
HR:	heart rate
IFCC:	International Federation of Clinical Chemistry and Laboratory Medicine
IMP:	investigational medicinal product
INN:	international nonproprietary name
IRT:	interactive response technology
ITT:	intent-to-treat
KM:	Kaplan-Meier
LLT:	lower level term
MACE:	major adverse cardiovascular events

MAR:	missing at random
MDRD:	modification of diet in renal disease
MedDRA:	Medical Dictionary for Regulatory Activities
MI:	multiple imputation
MNAR:	missing not at random
NIMP:	noninvestigational medicinal product
PCSA:	potentially clinically significant abnormality
PD:	pharmacodynamic
PK:	pharmacokinetic
PT:	preferred term
SAE:	serious adverse events
SBP:	systolic blood pressure
SD:	standard deviation
SOC:	system organ class
T2D:	type 2 diabetes mellitus
TEAE:	treatment-emergent adverse event
ULN:	upper limit of normal
WHO-DD:	World Health Organization-Drug Dictionary

## 1 OVERVIEW AND INVESTIGATIONAL PLAN

### 1.1 STUDY DESIGN AND RANDOMIZATION

This is a Phase 3, multicenter and multinational, randomized, double-blind, placebo-controlled, parallel-group study. Patients will be randomly assigned 1:1 to the following 2 treatment groups

- Sotagliflozin 400 mg.
- Placebo.

All patients will have a Screening Period comprised of an up to 2-week Screening Phase and a 2-week, single-blind placebo Run-in Phase prior to randomization. Following randomization, patients will have a 26-week, double-blind Core Treatment Period, a 53-week double-blind Extension Period, and a 2-week post-treatment Follow-up period to collect safety information (patients who prematurely discontinue the study treatment are expected to continue in the study).

At the end of the screening period, eligible patients will be centrally randomized (using permuted block randomization schedule) via an Interactive Response Technology (IRT). The randomization will be stratified by

- Hemoglobin A1c (HbA1c) at Screening ( $\leq 8.5\%$ ,  $> 8.5\%$ ).
- Metformin use at Screening (Yes, No).
- Systolic blood pressure (SBP) at Screening ( $< 130$  mmHg,  $\geq 130$  mmHg).

It is anticipated to randomize a total of approximately 500 patients.

### 1.2 OBJECTIVES

#### 1.2.1 Primary objectives

The primary objective of this study is to demonstrate the superiority of sotagliflozin 400 mg versus placebo on HbA1c reduction at Week 26 in patients with type 2 diabetes mellitus (T2D) who have inadequate glycemic control with a sulfonylurea alone or in combination with metformin.

#### 1.2.2 Secondary objectives

- To compare sotagliflozin 400 mg versus placebo for:
  - Change from Baseline in fasting plasma glucose (FPG) at Week 26,
  - Change from Baseline in body weight at Week 26,
  - Change from Baseline in SBP at Week 12 for patients with baseline SBP  $\geq 130$  mmHg,

- Change from Baseline in SBP at Week 12 for all patients,
- Proportion of patients with HbA1c <6.5%, <7.0% at Week 26.
- To evaluate the safety of sotagliflozin 400 mg versus placebo throughout the 79-week trial.

### 1.2.3 Other objectives

[figure not shown]
- To compare sotagliflozin versus placebo based on other blood pressure endpoints.
- To compare sotagliflozin versus placebo with respect to change from Baseline on the following endpoints:
  - Estimated glomerular filtration rate (eGFR),
  - Reduction in body weight by  $\geq 2\%$ ,  $\geq 5\%$ , and  $\geq 10\%$ .
- To compare sotagliflozin versus placebo for:
  - Change from Baseline in HbA1c at Week 79,
  - Change from Baseline in FPG at Week 79,
  - Change from Baseline in body weight at Week 79.
- To compare the use of rescue medications for hyperglycemia in the sotagliflozin and placebo treatment groups.
- To assess plasma concentrations of sotagliflozin and its 3-O-glucuronide metabolite.

### 1.3 DETERMINATION OF SAMPLE SIZE

The sample size/power calculations are based on the primary variable, change from Baseline to Week 26 in HbA1c. Assuming a common standard deviation (SD) of 1.2% and using a 2-sided test at a 0.05  $\alpha$ -level, 250 patients per arm will have 99% power to detect a treatment difference of 0.6% in mean HbA1c change from Baseline to Week 26 between sotagliflozin 400 mg and placebo.

The number of patients taking a sulfonylurea and metformin will be limited to 330 patients, to ensure sufficient numbers of sulfonylurea monotherapy patients.

### 1.4 STUDY PLAN

The study flowchart can be found in [Appendix D](#).

## 1.5 MODIFICATIONS TO THE STATISTICAL SECTION OF THE PROTOCOL

This section summarizes major changes to the protocol statistical section with emphasis on changes after study start (after the first patient was enrolled).

The protocol history table below gives the timing, rationale, and key details of major changes to the protocol statistical section.

The first patient was enrolled on Feb 24, 2017. There were no planned interim analyses.

**Table 1 - Protocol amendment statistical changes**

Amendment Number	Date Approved	Rationale	Description of statistical changes
2	20-Dec-2017	5 half-lives of sotagliflozin prolonged to 10 days considering patients with moderate renal dysfunction	5 half-lives of IMP updated from 5 days to 10 days; TEAE period updated accordingly
2	20-Dec-2017	Baseline eGFR defined as recommended by CDISC Therapeutic Area Data Standards User Guide for Diabetic Kidney Disease	For serum creatinine and eGFR, the baseline value is defined as the average of all values before the first dose of double-blind IMP for those randomized and exposed or before randomization for those who were randomized but never exposed to IMP.
2	20-Dec-2017	The effect in body weight is considered more closely associated with the planned indication	Change in the order of secondary objectives, endpoints and multiplicity considerations
2	20-Dec-2017	Urgent coronary revascularization not adjudicated by CEC to be consistent with outcome trials	Urgent coronary revascularization not included in adjudication related analyses
2	20-Dec-2017	AE leading to study discontinuation is less clinically relevant than AE leading to treatment discontinuation	Delete AEs leading to discontinuation from the study from safety endpoints
2	20-Dec-2017	To understand treatment effects over the entire study duration	Several objectives/endpoints "blood pressure endpoints at Week 26 and Week 79, HbA1c, FPG and body weight endpoints at Week 79" were added

## 1.6 STATISTICAL MODIFICATIONS MADE IN THE STATISTICAL ANALYSIS PLAN

The statistical analysis plan history table below gives the timing, rationale, and key details for major changes to the statistical analysis features in the statistical analysis plan. Changes also incorporated in a protocol amendment are cross-referenced to [Table 1](#).

Table 2 - Statistical analysis plan statistical changes

SAP version number	Date approved	Rationale	Description of statistical changes
1	07-Aug-2018	5 half-lives of sotagliflozin prolonged to 10 days considering patients with moderate renal dysfunction	5 half-lives of IMP updated from 5 days to 10 days; TEAE period updated accordingly*
1	07-Aug-2018	Baseline eGFR defined as recommended by CDISC Therapeutic Area Data Standards User Guide for Diabetic Kidney Disease	For serum creatinine and eGFR, the baseline value is defined as the average of all values before the first dose of double-blind IMP for those randomized and exposed or before randomization for those who were randomized but never exposed to IMP*
1	07-Aug-2018	The effect in body weight is considered more closely associated with the planned indication	Change in the order of secondary objectives, endpoints and multiplicity considerations*
1	07-Aug-2018	Urgent coronary revascularization not adjudicated by CEC to be consistent with outcome trials	Urgent coronary revascularization not included in adjudication related analyses*
1	07-Aug-2018	AE leading to study discontinuation is less clinically relevant than AE leading to treatment discontinuation	Delete AEs leading to discontinuation from the study from safety endpoints*
1	07-Aug-2018	To understand treatment effects over the entire study duration	Several objectives/endpoints "blood pressure endpoints at Week 26 and Week 79, HbA1c, FPG and body weight endpoints at Week 79" were added*
1	07-Aug-2018	Clarification on EOSI renal events	Details specified on renal events to be consistent with outcome studies in Section 2.1.4.2 .
1	07-Aug-2018	[REDACTED]	[REDACTED]
1	07-Aug-2018	[REDACTED]	[REDACTED]
1	07-Aug-2018	Updating the wording to be consistency with CEC charter	Unstable angina leading to hospitalization changed to Unstable angina requiring hospitalization
2	03-Jun-2019	[REDACTED]	[REDACTED]
2	03-Jun-2019	Number of iterations for multiple imputation was changed	Number of iterations for multiple imputation was changed from 10 000 to 2000
2	03-Jun-2019	Wording change to be consistent with CEC charter	"Heart failure leading to hospitalization" changed to "Heart failure requiring hospitalization"
2	03-Jun-2019	MedDRA version and dictionary updated	MedDRA version was updated to V22.0 and list of PTs for selected EOSI were updated
3	This version	[REDACTED]	[REDACTED]

---

SAP version number	Date approved	Rationale	Description of statistical changes
			[REDACTED]
3	This version	[REDACTED]	[REDACTED]
3	This version	[REDACTED]	[REDACTED]
3	This version	[REDACTED]	[REDACTED]
3	This version	[REDACTED]	[REDACTED]

---

\* Change made in Protocol Amendment 2 dated 20-Dec-2017.

## 2 STATISTICAL AND ANALYTICAL PROCEDURES

### 2.1 ANALYSIS ENDPOINTS

#### 2.1.1 Demographic and baseline characteristics

The baseline value for all variables (with the exception of serum creatinine and eGFR) is defined as the last available value before the first dose of double-blind investigational medicinal product (IMP), or the last available value prior to randomization for patients who were randomized but never exposed to IMP.

For serum creatinine and eGFR, the baseline value is defined as the average of all values before the first dose of double-blind IMP for those randomized and exposed or before randomization for those who were randomized but never exposed to IMP.

Baseline safety and efficacy parameters are presented along with the summary statistics for safety and efficacy sections ([Section 2.4.4](#) and [Section 2.4.5](#)).

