6.1.1.2 Run-in phase (Visit 2)

The Run-in phase will last 2 weeks. Patients will be treated in a single-blind manner with placebo (2 tablets) once daily during the Run-in phase, starting from Visit 2.

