10.1.1.1.1 On-site Visit 1 (Week -4) Screening Visit

The following procedures/assessments will be performed at Visit 1 (Week -4):

- [REDACTED]
- [REDACTED]
- [REDACTED]
- [REDACTED]

- Concomitant medication and medication history, including any prior medications for T2D
- Complete physical examination including height, weight, and vital signs (SBP and DBP, temperature, heart rate, and respiratory rate). After 5 minutes resting, seated SBP, DBP, and heart rate will be assessed 3 times with at least 1 minute between each measurement (see [Appendix C](#) for details)
- IRT to be notified (allocation of ID, registration of screening)
- Assessment of all inclusion/exclusion criteria
- Collection of demographic data (age, gender, race, and ethnic origin)

- Assessment of the patient's medical and surgical history: to include history of T2D, treatment and complications (eye, kidney, amputations, etc); history of smoking/tobacco use; history of alcohol and drug abuse
- Patient diary is dispensed and instructions/training are provided
- 12-lead ECG
- The following laboratory testing (by the central laboratory):
 - Fasting plasma glucose
 - HbA1c
 - Hepatitis serology
 - Serum pregnancy testing for WOCBP or serum FSH and estradiol for postmenopausal women
 - Hematology
 - Clinical chemistry to include amylase and lipase
 - Fasting lipids
 - Urinalysis (dipstick and microscopy)
- Patients are instructed to return to the site for Visit 2 (Week -2)

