10.1.1.2.1 On-site Visit 2 (Run-in, Week -2)

The following procedures/assessments will be performed at Visit 2 (Week -2):

- Measurement of body weight
- Abbreviated physical examination including vital signs (SBP and DBP, and heart rate). After 5 minutes resting, seated SBP, DBP, and heart rate will be assessed 3 times with at least 1 minute between each measurement (see [Appendix C](#) for details)
- Diet and exercise instruction
- Blood glucose meter is dispensed and instructions/training are provided
- Instruction on basic GU hygiene and hydration (see [Appendix B](#))
- IRT to be notified (registration of run-in, allocation of single-blind run-in kit)
- Patient diary is collected/reviewed and a new diary dispensed. Instruction/training is provided as needed
- AEs/SAEs/AESI/EOSI and hypoglycemia occurring since Visit 1 (if any) are reported.
- Run-in kit/placebo is dispensed
- Changes in concomitant medication are reported
- Fasting SMBG is assessed
- Patients are instructed to return to the site in the fasting state for Visit 3 (Randomization)

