#### **2.4.4.2 Analyses of secondary efficacy endpoints**

For continuous secondary efficacy parameters with missing data at baseline, missing baseline data will be imputed using MI under the missing at random (MAR) assumption. Missing data at baseline will be imputed using regression method that includes randomization stratum of HbA1c

( $\leq 8.5\%$ ,  $> 8.5\%$ ), randomization stratum of metformin use at Screening (Yes, No), randomization stratum of SBP ( $< 130$  mmHg,  $\geq 130$  mmHg), and baseline value in the imputation model..

Each continuous secondary efficacy endpoint (Section 2.1.3.2) will be analyzed using a similar ANCOVA model including the measurements at baseline and endpoint (observed or imputed). The missing data at endpoint will be imputed by the retrieved dropouts if there are at least 5 patients in each study treatment group who discontinued but have the endpoint. Otherwise, the washout imputation method will be used according to the criterion described in Section 2.4.4.1. After the imputation, each of the complete datasets will be analyzed by an ANCOVA model.

The ANCOVA model will include treatment groups (sotagliflozin 400 mg, placebo), randomization stratum of HbA1c ( $\leq 8.5\%$ ,  $> 8.5\%$ ), randomization stratum of metformin use at Screening (Yes, No), randomization stratum of SBP ( $< 130$  mmHg,  $\geq 130$  mmHg), and country as fixed effects, and the corresponding baseline secondary endpoint value as a covariate. For the analysis of SBP in patients with baseline SBP  $\geq 130$  mmHg, the randomization stratum of SBP will not be included in the ANCOVA model. Results from each complete dataset will be combined using Rubin's formula to provide the adjusted mean change from Baseline to Week 26 (or Week 12 for SBP) for each treatment group, as well as the between-group difference (comparing sotagliflozin 400 mg versus placebo) and the 95% CI for the difference.

For all continuous secondary endpoints, summary statistics at scheduled visits will be provided for each treatment group. The summary will include the number of observations, mean, SD, SE, minimum, median, and maximum. Graphical presentations will also be used to examine trends over time using mean values ( $\pm$ SE) and mean changes from baseline ( $\pm$ SE) at each of the scheduled visits. In addition, SBP will be summarized descriptively at each visit for those patients with baseline SBP  $\geq 140$  mmHg.

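### Adding the Screening and Run-in SBP readings as a covariate would modestly sharpen the two Week 12 SBP tests at almost no cost

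*SAP*

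**What the plan says.** - **Baseline.** SAP 2.1.1, repeated in SAP 2.5.4 and matching Protocol 11.4: "The baseline value for all variables (with the exception of serum creatinine and eGFR) is defined as the last available value before the first dose". For creatinine and eGFR, by contrast, "the baseline value is defined as the average of all values before the first dose of double-blind IMP".
- **Measurements before active drug.** SBP is taken at Visit 1 (Protocol 10.1.1.1.1), at Visit 2 (Protocol 10.1.1.2.1: "seated SBP, DBP, and heart rate will be assessed 3 times with at least 1 minute between each measurement") and at Visit 3 on Day 1 (Protocol 10.1.2.1). The run-in that starts at Visit 2 is on placebo (Protocol 6.1.1.2: "Patients will be treated in a single-blind manner with placebo (2 tablets) once daily during the Run-in phase").
- **Visit value.** Protocol Appendix C: "The mean of the 3 seated BPs will constitute the BP value for that visit". Nothing in either document averages SBP across visits.
- **Model.** SAP 2.4.4.2 fits an ANCOVA with treatment, the three randomisation strata "and country as fixed effects, and the corresponding baseline secondary endpoint value as a covariate". In the analysis of patients with baseline SBP of at least 130 mmHg, the SBP stratum is removed.
- **Role.** The two Week 12 SBP endpoints are steps 3 (subset) and 4 (all patients) of the fixed sequence in SAP 2.4.4.4. HbA1c below 7.0% is step 5.

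**The concern.** A single visit is a noisy measure of a patient's usual SBP. Averaging three readings within one sitting does not remove variation from one visit to the next. Two further pre-randomisation visit means are already in the database, and the SBP models make little use of them. The all-patients model sees Visit 1 only as above or below 130 mmHg. The subset model, which is tested first and in fewer patients, normally sees neither Visit 1 nor Visit 2.

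At stake is the width of the confidence intervals at steps 3 and 4. Failure at either step also stops the formal test of HbA1c below 7.0%. The sample size was set on HbA1c alone, and neither document states power for SBP.

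**Working it through.** **The plan's own figure.** The only stated power is for HbA1c: 250 per arm, difference 0.6%, SD 1.2%, two-sided 0.05, giving 99% (SAP 1.3). Check: SE = 1.2 × √(2/250) = 0.107; 0.6/0.107 − 1.96 = 3.63; power 99.99%. The figure reproduces, but it says nothing about SBP.

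**Assumed SBP inputs (none is in the documents).** Mean 130 mmHg. Between-patient SD / visit-to-visit SD of 12/8, 12/10 or 10/10 mmHg. Write B and W for the two variances and T = B + W. The correlation between two visits, B/T, is then 0.69, 0.59 or 0.50. Missing data and country are ignored.

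**Case 1: every pre-treatment visit predicts Week 12 equally well.** In the subset model, which has no stratum term, the residual variance of Week 12 SBP is:
- Day 1 covariate only: T − B²/T
- with the Visit 1-2 mean added: W + B(W/3)/(B + W/3)

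For 12/8 these are 208 − 144²/208 = 108.3 and 64 + 144 × 21.33/165.33 = 82.6. Simulation of 2,000,000 patients gives 108.0 and 82.4. The all-patients model contains a dichotomised Visit 1 value, so its figures come from simulation only.

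| SDs | All patients | SE change | Subset | SE change |
|---|---|---|---|---|
| 12/8 | 99.5 → 82.4 | −9% | 108.0 → 82.4 | −13% |
| 12/10 | 147.1 → 126.9 | −7% | 158.7 → 126.9 | −11% |
| 10/10 | 140.6 → 125.1 | −6% | 150.1 → 125.2 | −9% |

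The SE change is √(after/before) − 1. If the stratum were kept in the subset model, the variance gain would still be 11-17%, so the benefit does not arise only from dropping it.

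**Case 2: correlation decays with time.** Let the between-patient component lose 1.5% of its correlation per week, with visits at Weeks −4, −2, 0 and 12. Worked for the subset with 12/10, where M is the Visit 1-2 mean:
- Cov(Week 12, Day 1) = 144 × 0.985¹² = 120.1. Day 1 only: 244 − 120.1²/244 = 184.9.
- Var(M) = (2 × 244 + 2 × 144 × 0.985²)/4 = 191.9; Cov(M, Day 1) = 144 × (0.985⁴ + 0.985²)/2 = 137.6; Cov(M, Week 12) = 144 × (0.985¹⁶ + 0.985¹⁴)/2 = 114.8.
- The coefficients are 0.260 (Day 1) and 0.412 (M). Residual variance = 244 − 0.260 × 120.1 − 0.412 × 114.8 = 165.5.
- SE change: √(165.5/184.9) − 1 = −5.4%.

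Over all three SD pairs, decay of 1.5% per week gives SE reductions of 3-4% (all patients) and 5-6% (subset). Decay of 3% per week gives about 2% and 3%. The Case 1 figures are therefore an upper range.

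**What this means for the tests.** Power = Φ(δ/√(2v/n) − 1.96), where v is the residual variance and n the number per arm.
- Subset, assumed 125 per arm, 4 mmHg, Case 1: 71-86% rises to 80-94%. For 12/10: 4/√(2 × 159.0/125) − 1.96 = 0.55, or 71%; with v = 127.1, 0.85, or 80%.
- The same with 1.5% decay and 12/10: v = 184.9 gives 64%; v = 165.5 gives 69%.
- Subset, assumed 75 per arm, 10 mmHg: at least 99.8% without the covariate.
- All patients, 250 per arm, Case 1: at 5 mmHg, at least 99.6% without the covariate; at 3 mmHg with 12/10, 79% (v = 147.1) rises to 85% (v = 126.9).

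**The case against.** The strongest reply is that nothing here is wrong. Protocol and SAP agree on the baseline definition, each visit value is already a mean of three readings, and the ANCOVA adjusts for Day 1 SBP. The only SBP effect in the documents is 10-15 mmHg in patients at or above 130 mmHg (Protocol 4.5), and at that size the subset test succeeds with or without the extra covariate. All of this stands, and it limits the point to an optional improvement. It does not dispose of it: Protocol 4.5 also reports little effect below 130 mmHg, so the all-patients effect at step 4 should be smaller, and no SBP power is given.

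A second reply concerns imputation. The models in SAP 2.4.4.1 use only the strata and baseline, and the retrieved-dropout model is kept simple because it may rest on as few as 5 patients per arm. A covariate in the analysis model only would make the two models differ. They already differ, since country is in the ANCOVA but not in the imputation models. The fix must still say what happens there and with missing Visit 1 or 2 values.

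Third, antihypertensive doses are explicitly held constant only for the 12 weeks after randomisation (Protocol 8.8.1), so earlier readings may reflect another regimen. That would lower the gain. It cannot bias the comparison, because the covariate is fixed before randomisation and the model sets its weight.

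A reader might also infer that the plan is inconsistent because it averages creatinine and eGFR but not SBP. The documents do not support that: SAP 1.5 attributes the averaging to a data standard for diabetic kidney disease, not to a general rule on precision.

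**Conclusion.** The point holds as a modest, avoidable loss of precision in two confirmatory analyses. Under the assumed SDs, the standard error could fall by 6-9% (all patients) and 9-13% (subset) at best, and by about 2-4% and 3-6% if correlation decays by 1.5-3% per week. The direction is the same throughout; the size depends on variances and correlations that the documents do not give. The gain could change a test result only for effects well below the Phase 2 figure, roughly 5 mmHg or less in the subset and 3 mmHg overall.

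Two stronger readings are tempting and not supported. The first is that a single-visit baseline biases the SBP result, especially in a subset selected on that value. Regression to the mean enlarges the within-arm falls in the subset, but it acts on both randomised arms alike and leaves their difference valid. The second is that the fixed sequence is likely to fail at the SBP steps. Nothing in the documents shows this, and at 10-15 mmHg the subset result would not change.

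**What to change.** Before unblinding, add to SAP 2.4.4.2, for both Week 12 SBP analyses:
- a second continuous covariate beside Baseline SBP, namely the mean of the available Visit 1 and Visit 2 SBP values, or the one value if only one exists;
- a statement that the change score, the subset definition (baseline SBP of at least 130 mmHg) and the randomisation strata are unchanged.

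In SAP 2.4.4.1, include the covariate in the washout imputation model for SBP, and in the retrieved-dropout model where the number of retrieved dropouts supports it. Record the change in SAP 1.6, since Protocol 11.4.2.2 describes the ANCOVA without this term.

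Cost: one degree of freedom per model and a slightly larger imputation model. The earlier readings may predict less well if the antihypertensive regimen changed. No new data, visits or patients are needed.
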